2.1 Study objectives

[The aim of this trial is to evaluate the superiority of combined VLCKD, intensive lifestyle intervention and naltrexone/bupropion versus standard of care with naltrexone/bupropion on weight loss.]

2.2 Primary Endpoints

[figure not shown]
[Weight loss percentage at 26 weeks; calculated as: (weight at 26 weeks – baseline weight)/baseline weight.]

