2.3 Secondary Endpoints

- A weight loss percentage at 10 weeks, 16 weeks and at end of trial (= 52 weeks from start)
- A proportion of patients with a weight loss percentage of 5% or more at 10, 16, 26 and 52 weeks
- A proportion of patients with a weight loss percentage of 10% or more at 10, 16, 26 and 52 weeks
- The time to reach a weight loss percentage of 5% and 10%
- The dose of naltrexone/bupropion used at 10, 16, 26 and 52 weeks and at the end of the trial
- The tolerability of VLCKD and NB
- Adherence to VLCKD and NB
- The Patient-Reported Outcome Measures (PROMs) of hunger and cravings at 0, 4, 10, 16, 26 and 52 weeks
- The change in fasting glucose, lipids and blood pressure at 10, 16, 26 and 52 weeks]

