5.1.5 Pharmacovigilance

Any adverse reactions related to the medicinal products used by the participants in the study, can be reported to the Marketing Authorisation Holder and/or the Competent Authorities according to the pharmacovigilance guidelines.

6 Statistics and Data Analysis

Statistical analysis will be performed in accordance with ICH E9; a detailed description of the analysis is provided in the Trial-specific Statistical Analysis Plan (SAP). ICH E3 and E8 will guide the structure and content of the clinical trial report.

[The hypothesis for this trial is that the percentage of weight loss will be greater for the experimental arm than the comparator arm.]

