6.1 Sample Size Determination

The sample size was determined for a two-sided two-sample t-test to test the difference in mean weight loss percentage between both treatment arms, assuming a mean weight loss of 6.75% (SD 7.12%) [unpublished, own retrospective data] in the control arm and a mean weight loss of 12% (SD 5.3) [unpublished, data provided by Pro Well] in the intervention arm. Assuming a 20% drop-out rate, a 5% significance level and 80% of power, a total sample size of 62 patients is indicated, or 31 patients per study arm

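### The formula for the primary endpoint subtracts in the wrong order, so a weight loss comes out negative

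*Protocol*

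**What the plan says.** Section 2.2 of the protocol labels the primary endpoint "Weight loss percentage at 26 weeks" and states that it is "calculated as: (weight at 26 weeks – baseline weight)/baseline weight". This is the only calculation rule for the endpoint in the protocol. The synopsis repeats the endpoint without a formula.

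Four other places use the same quantity with a loss counted as positive:

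- Section 2.3 has two responder endpoints, "A proportion of patients with a weight loss percentage of 5% or more at 10, 16, 26 and 52 weeks" and "A proportion of patients with a weight loss percentage of 10% or more at 10, 16, 26 and 52 weeks".
- Section 2.3 also has the time to reach a loss of 5% and of 10%.
- The opening of section 6 gives the hypothesis that "the percentage of weight loss will be greater for the experimental arm than the comparator arm".
- Section 6.1 plans for mean losses of 6.75% (SD 7.12%) in the comparator arm and 12% (SD 5.3) in the experimental arm.

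Section 6.2 asks for the arm means and the mean difference in weight loss percentage, each with a 95% confidence interval, and tests the difference with a two-sided two-sample t-test.

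**The concern.** The label and the formula in section 2.2 contradict each other. Follow-up minus baseline, divided by baseline, measures change, and a loss is a negative change. No other part of the protocol reverses the order or says that absolute values are taken.

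The primary endpoint is the quantity a protocol most needs to fix without ambiguity, because programmers and later readers work from the formula. If it is coded as written, the arm means, their difference and the confidence limits carry the wrong sign for an endpoint called weight loss. The estimated effect then points against the stated hypothesis when the diet works as planned. If the same derivation is reused for the endpoints in section 2.3, patients who gain weight would count as responders.

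**Working it through.** **Inputs.** Formula: section 2.2. Thresholds: section 2.3. Direction of the hypothesis: opening of section 6. Means, SDs, 20% drop-out, 5% two-sided level, 80% power and 31 patients per arm: section 6.1. The 100 kg baseline is an example only; the formula gives a ratio, so the choice does not matter.

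**1. The plan's own sample size.** Difference = 12 - 6.75 = 5.25 points. Common SD = sqrt((7.12² + 5.3²)/2) = 6.28.

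- Normal approximation: 23 per arm.
- Noncentral t: 24 per arm, power 0.810.
- Drop-out: 24/0.8 = 30 per arm, 60 in total.

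The stated 62 is within two patients of this, so the planning values can be taken as they stand.

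**2. The formula applied to single patients.** Let W0 be baseline weight and W26 the weight at week 26. As written, the endpoint is (W26 - W0)/W0.

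- 100 kg to 88 kg: (88 - 100)/100 = -12%
- 100 kg to 95 kg: (95 - 100)/100 = -5%
- 100 kg to 105 kg: (105 - 100)/100 = +5%

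**3. The formula applied to the planning means.**

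| Arm | Weight after the planned mean loss from 100 kg | As written | With the order reversed |
|---|---|---|---|
| Comparator | 93.25 kg | -6.75% | +6.75% |
| Experimental | 88 kg | -12% | +12% |
| Experimental minus comparator | | -5.25 points | +5.25 points |

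As written, the experimental arm has the smaller value. The hypothesis says it should have the greater one. Taking the difference the other way round does not help, because the arm values themselves are in the wrong order.

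**4. What does not change.** Expected completers per arm = 31 × 0.8 = 24.8.

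- SE = sqrt((7.12² + 5.3²)/24.8) = 1.78
- |t| = 5.25/1.78 = 2.95 on 2 × 24.8 - 2 = 47.6 degrees of freedom
- If the planning values are observed, two-sided p = 0.005 and the 95% confidence interval is 7.2 points wide
- Power = 0.82

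All of these are the same for +5.25 and -5.25.

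**5. If the formula were reused in section 2.3.** This assumes normally distributed outcomes with the planning means and SDs.

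| Threshold | Arm | Share counted, as written | Share counted, as intended |
|---|---|---|---|
| 5% or more | Comparator | 4.9% | 59.7% |
| 5% or more | Experimental | 0.07% | 90.7% |
| 10% or more | Comparator | 0.9% | 32.4% |
| 10% or more | Experimental | 0.002% | 64.7% |

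As written, those counted would be patients who gained weight, and the comparison between arms would reverse. Section 2.3 speaks of loss, so this reading is not expected. The table shows only what a mechanical application would produce.

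**The case against.** The best defence is that nothing inferential depends on the sign. The test is two-sided, and the p-value, power and sample size stay the same. The intent is also plain. The endpoint is called a loss, every other section speaks of loss in positive terms, and a change of -12% is readily reported as a 12% loss. A reader shown -12% against -6.75% would still say that the first arm lost more. The formula is attached only to the week 26 endpoint, and section 2.3 neither restates it nor refers back to it. The protocol also leaves analysis detail to a statistical analysis plan, which is not at hand and may set the sign correctly.

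Most of this stands, and it is why the point ranks low. The conclusion on superiority would not change, and wrong responder counts are unlikely in practice. It does not make the formula right, however. The protocol does not leave the derivation open; it states one. An analysis plan that follows the protocol inherits the error, and one that reverses the order departs from the protocol's definition of its primary endpoint. That the intent is clear makes the correction uncontroversial, not unnecessary.

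**Conclusion.** The concern holds. The calculation rule for the primary endpoint is wrong as written: it gives a negative number for what the protocol calls a weight loss, and it conflicts with the thresholds, the hypothesis and the planning means.

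The size is limited to sign and direction. At the planning values, the reported difference (experimental minus comparator) would be -5.25 rather than +5.25 percentage points, with the confidence limits reflected in the same way. This follows from the formula and needs no distributional assumption. The p-value, power and interval width in the check do rest on the planning means and SDs and on 24.8 completers per arm; that they are the same under either sign does not. Only the responder shares assume normality, and they describe a reading that is not expected. This is a correction worth making, not a threat to the primary analysis.

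**What to change.** In section 2.2, define weight loss percentage as 100 × (baseline weight - weight at the visit)/baseline weight, and state that positive values are losses. Apply this one definition wherever the term appears: the primary endpoint at week 26, the other visits, the 5% and 10% responder endpoints, and the time to reach each threshold. The factor of 100 is included because the present formula returns a fraction, while the thresholds and planning means are given in per cent.

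The cost is an edit to one formula and one added sentence. Data collection, the t-test, the power and the sample size of 62 are untouched.

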2.3 Secondary Endpoints

- A weight loss percentage at 10 weeks, 16 weeks and at end of trial (= 52 weeks from start)
- A proportion of patients with a weight loss percentage of 5% or more at 10, 16, 26 and 52 weeks
- A proportion of patients with a weight loss percentage of 10% or more at 10, 16, 26 and 52 weeks
- The time to reach a weight loss percentage of 5% and 10%
- The dose of naltrexone/bupropion used at 10, 16, 26 and 52 weeks and at the end of the trial
- The tolerability of VLCKD and NB
- Adherence to VLCKD and NB
- The Patient-Reported Outcome Measures (PROMs) of hunger and cravings at 0, 4, 10, 16, 26 and 52 weeks
- The change in fasting glucose, lipids and blood pressure at 10, 16, 26 and 52 weeks]

2.4 Study design

This is a parallel multicentric longitudinal randomized controlled trial in which prospective data will be collected from the electronic health record. The inclusion and exclusion criteria will be checked and afterwards patients will be randomized to (unblinded) medication only or combination with VLCKD. Both groups include NB and lifestyle changes for 26 weeks but the patients belonging to the experimental group must follow a VLCKD in the first 10 weeks on top of it. Like the other group, the remaining 16 weeks will consist of NB combined with lifestyle interventions. Afterwards there is a follow-up extension of 26 weeks. See appendix 4 for detailed overview of clinical and biochemical parameters to be collected during the trial.

2.5 Expected duration of the Study

[This trial will have a duration of 2 years in total. 1 year is taken into account to include the patients into the study according to the inclusion and exclusion criteria. Afterwards patients will be randomly inserted into the comparator arm (NB + lifestyle interventions) or experimental arm (NB + Lifestyle interventions + VLCKD). Both arms of the study design will be evaluated for 52 weeks. 26 weeks will consist of the treatment after which another 26 weeks will be used as a follow-up extension.]

The End of Study is defined as Last Patient Last Visit (LPLV). The CI shall notify the EC of the end of the Study. The CI will submit a final report with the results of the study, including any publications/abstracts, to the EC within 1 year of study termination.

The Sponsor or EC can decide to halt or prematurely terminate the Study when new information becomes available whereby the rights, safety and well-being of Study participants can no longer be assured, when the integrity of the Study has been compromised, or when the scientific value of the Study becomes obsolete and/or unjustifiable]

3 Study Population / Eligibility Criteria

3.1 Inclusion criteria[]

Participants eligible for inclusion in this Trial must meet **all** of the following criteria:

1. Voluntary written informed consent of the participant or their legally authorized representative has been obtained prior to any screening procedures
2. Use of highly effective methods of birth control; defined as those that, alone or in combination, result in low failure rate (i.e., less than 1% per year) when used consistently and correctly; such as implants, injectables, combined oral contraceptives, some IUDs, true sexual abstinence (i.e. refraining from heterosexual intercourse during the entire period of risk associated with the Trial treatment(s)) or commitment to a vasectomised partner.
3. [Minimum 18 years of age at the time of Informed Consent signature]
4. Underwent bariatric surgery (RYGB or SG) with weight regain $\geq 10\%$ of nadir weight
5. People without Type 2 diabetes (T2D)
 - No history, no drugs, HbA1c < 6,5% and FPG <126 mg/dl)

All participants that are considered for Trial participation, per the above criteria will be documented on the Screening Log, including Screen Failures.

3.2 Exclusion criteria

Participants eligible for this Trial must **not** meet any of the following criteria:

1. Participant has a history of [type 2 diabetes mellitus (also drugs, HbA1c > 6,5% and FPG >126 mg/dl)]
2. [Female who is pregnant, breast-feeding or intends to become pregnant or is of child-bearing potential and not using an adequate, highly effective contraceptive]
3. Participation in an interventional Trial with an investigational medicinal product (IMP) or device
4. [Not willing to sign informed consent]
5. Younger than 18 years of age at the time of Informed Consent signature
6. Other types of bariatric surgery other than RYGB or SG (including LAGB, BPD)
7. Underwent bariatric surgery (RYGB or SG) with weight regain $< 10\%$ of nadir weight
8. Contraindication for VLCKD, including CKD stage 4-5, liver cirrhosis, type 1 diabetes mellitus, active gout
9. Contraindication for NB including the use of opioids, history of CNS tumor or seizures, severe psychiatric disorder or > 2 psychotropic medications, uncontrolled hypertension
10. Use of other drugs for weight management (e.g. GLP1Ra) in the last 3 months prior to trial intervention
11. Any disorder, which in the Investigator's opinion might jeopardise the participant's safety or compliance with the protocol]

Participants who meet one or more of the above exclusion criteria **must not proceed** to be enrolled/randomized in the Trial and will be identified on the Screening Log as Screen Failure.

4 Study Procedures

4.1 Participant consent and withdrawal of consent

The Study will be conducted only on the basis of prior informed consent by the Study participants and/or their legally authorized representative(s). As such, no Study-related procedures will be conducted prior to obtaining written informed consent from potential Study participants.

The process for obtaining and documenting initial and continued informed consent from potential Study participants will be conducted in accordance with ICH-GCP E6(R2), applicable regulatory requirements and internal Standard Operating Procedures (SOPs).

All originally signed obtained Informed Consent Forms (ICFs) must be retained/archived in the Investigator Site File (ISF) at the Participating Site and must not be destroyed (even when a scanned copy is available) before expiration of the legal archiving term as defined in the protocol section entitled "Archiving".

Participants may voluntarily withdraw consent to participate in the Study for any reason at any time. The participant's request to withdraw from the Study must always be respected without prejudice or consequence to further treatment. Consent withdrawal will be documented in the participant's medical record.

Study data and samples collected before withdrawal can be used in the study. No new study data or samples will be collected after withdrawal of the participant.

4.2 Selection of Participants / Recruitment

Potential participants will be identified and recruited during patient consultations in one of the participating sites. No additional recruitment material (such as for example flyers, social media advertising, audio/video recordings) will be used.

4.3 Randomization Procedure

To ensure the integrity of the Study, the following randomization procedures have been established:

During the initial study visit, participants will be randomized in a 1:1 ratio to either the experimental arm (with VLCKD) or the comparator arm (without VLCKD), while receiving naltrexone/bupropion and lifestyle intervention. Allocation to one of these two groups will be conducted using a central randomization procedure accessible in the eCRF (RedCap). A computer-generated block randomization schedule will be created using the PLAN procedure in SAS software.

A randomization list will be prepared by the Sponsor's designated staff, not involved in recruiting Study participants, medical care, drug administration or follow-up.

4.4 Premature discontinuation

Participants may voluntarily discontinue from Study treatment and/or prematurely end their participation in the Study for any reason at any time. In such case the Investigator must make a reasonable effort to contact the participant (e.g. via telephone, e-mail, letter) in order to document the primary reason for this decision.

The Investigator may also decide at any time during the course of the Study, to temporarily interrupt or permanently discontinue the Study treatment if it is deemed that continuation would be detrimental to, or not in the best interest of the participant.

For participants whose status is unclear because they fail to appear for Study visits without stating an intention to discontinue or withdraw, the Investigator must make every effort to demonstrate "due diligence" by documenting in the source documents which steps have been taken to contact the participant to clarify their willingness and ability to continue their participation in the Study (e.g. dates of telephone calls, registered letters, etc.).

A participant should not be considered lost to follow-up until due diligence has been completed.

4.5 By visit

There are five scheduled in-clinic visits, each involving a blood draw. Among these, three visits are routine for naltrexone/bupropion, which include the initial intake and visits after 16 and 52 weeks. The study-specific visits occur at 10 weeks and 26 weeks. During the routine visits, only fasting glucose and lipid levels (LDL-cholesterol, HDL-cholesterol, triglycerides) will be assessed in the blood. However, during the study-specific visits, in addition to fasting glucose and lipids, the following parameters will also be examined in the blood: Hemoglobin A1c, liver function (AST, ALT, gamma-GT, alkaline phosphatase, total bilirubin, albumin), kidney function (creatinine, eGFR), thyroid function (TSH, free T4), and uric acid. For a detailed overview of the visit schedule, please refer to the Study Flowchart.

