A PhD student will be part-time (50%) appointed for this trial. He/she will be accountable for both sites (AZ Sint-Jan Brugge & UZ Leuven). The financial remuneration will be split between Goodlife Pharma and Pro Well. The PhD student will assist with

- Recruitment of patients: The PhD student will have access to the medical records of the patients of UZ Leuven and to the pseudomized data of AZ Sint-Jan Brugge by using Redcap.
- Data collection and monitoring
- Planning and monitoring
- Adverse event reporting
- Scientific report writing and dissemination

Goodlife Pharma

The pharmaceutical company (Goodlife Pharma) will provide the “Study drugs” (MYSIMBA) free of charge. For this multicenter study, Goodlife Pharma will supply the coordinating site (UZ Leuven) as well as the participating site (AZ Sint-Jan Brugge).

Pro Well

The study diet (VLCKD) and lifestyle program will be provided by the Company (Pro Well). For this multicenter study, Pro Well will supply the coordinating site (UZ Leuven) as well as the participating site (AZ Sint-Jan Brugge).

Both Goodlife Pharma as Pro Well

No payments other than those explicitly foreseen shall be made by Company to Institution with respect to the Study, unless agreed in writing. Such agreement must be executed by authorised personnel, must include a specific statement of any fees or costs to be paid and the reasons for payment, and must be attached as an annex to this Agreement.

An overview of the budget is displayed on the next page.

Budget

Items/Staff	Per unit Cost	Quantity	Total
VLCKD	-	-	Provided by Pro Well
Lifestyle program	-	-	Provided by Pro Well
Mysimba tablets	-	-	Provided by Goodlife Pharma
PhD student (50%)	-	-	Split between Pro Well and Goodlife Pharma
Pregnancy test	€ 10.00	20 tests	€ 200.00 by Internal fund (KUL/UZ Leuven krediet)
UZ Leuven			
Study specific lab tests (fasting glucose, lipids)	€ 10.86	62 samples	€ 673.32 by Internal fund (KUL/UZ Leuven krediet)
Pharmacy transit	€ 2,426.40	1 site	€ 2,426.40 by Internal fund (KUL/UZ Leuven krediet)
AZ Sint-Jan Brugge			
Study specific lab tests (fasting glucose, lipids)	€ 21.54	62 samples	€ 1,335.48 by Internal fund (KUL/UZ Leuven krediet)
Start-up fee	€ 250.00	1	€ 250.00 by Internal fund (KUL/UZ Leuven krediet)
Annual fee	€ 100.00	2 years	€ 200.00 by Internal fund (KUL/UZ Leuven krediet)
Pharmacy transit	€ 340.00	1 site	€ 340.00 by Internal fund (KUL/UZ Leuven krediet)
Total			€ 5,425.20

ROLES AND RESPONSIBILITIES

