Procedures/assessments	Phase 0: Screening and randomization		Phase 1: Lifestyle + NB with vs without VLCKD							Phase 2: Lifestyle + NB (all participants)				Follow-up (all participants)		
	Screening (In-clinic)	Randomization (in-clinic)	Remote	Remote	Remote	Remote	Remote	Remote	In-clinic (study specific)	Remote	Remote	In-clinic (Routine)	Remote	Remote	In-clinic (study specific)	In-clinic (routine)
Visit	V1	V2	V3	V4	V5	V6	V7	V8	V9	V10	V11	V12	V13	V14	V15	V16
Timing of visits (weeks)		Start	Start	W3	W4	W6	W8	W10	W10	W12	W16	W16	W20	W26	W26	W52
Visit window (days)									±30			±30			±30	±30
Lifestyle program			X		X		X			X	X		X	X		
Naltrexone/bupropion (NB)		X							X			X			X	X
VLCKD			(X) ¹	(X) ¹	(X) ¹	(X) ¹	(X) ¹	(X) ¹								
Screening assessments and randomization																
Informed consent	X ²															
Inclusion/exclusion criteria	X	X														
Randomization		X														
Anthropometric data (height, weight, waist circumference)		X							X			X			X	X

Clinical examination (Blood pressure, heart and lung auscultation, abdominal palpitation and percussion)		X							X			X				X	X
Laboratory tests																	
Fasting glucose		X							X			X				X	X
Hemoglobin A1c		X										X					X
Lipids: LDL-cholesterol, HDL-cholesterol, triglycerides		X							X			X				X	X
Liver test: AST, ALT, gamma-GT, alkaline phosphatase, total bilirubin, albumin		X										X					X
Kidney function: creatinine, eGFR		X										X					X
Thyroid function: TSH, free T4		X										X					X
Uric acid		X										X					X
Questionnaires																	
The PsyEndoAUDIT questionnaire ³		X							X			X				X	X
The PsyEndoCIDI questionnaire ³		X							X			X				X	X
The PsyEndoEDE questionnaire ³		X							X			X				X	X
The PsyEndoHADS questionnaire ³		X							X			X				X	X
Nederlandse vragenlijst voor eetgedrag ³		X							X			X				X	X
The ObesitasIPAQ questionnaire ³		X							X			X				X	X

The quality of life (SF-36) questionnaire ³		X							X				X			X	X
The outtake questionnaire															X		
Reason for discontinuation		X							X			X			X	X	
(Serious) Adverse event (S)(AE) assessment		X							X			X			X	X	

- Depending on randomization in either intervention (with VLCKD) or comparator group (without VLCKD).
- Informed Consent must be obtained prior to performing any other Trial-related procedures as part of the standard of care.
- See appendix 4 for the respective questionnaires.

I Background and Rationale

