8.4 Protocol / GCP compliance

The Study must be performed in accordance with the protocol, current ICH and ICH-GCP guidelines, and applicable regulatory and country-specific requirements. ICH guidelines are an international ethical and scientific quality standard for designing, conducting, recording, and reporting studies that involve the participation of human participants. Compliance with this standard provides public assurance that the rights, safety, and well-being of Study participants are protected, consistent with the principles that originated in the most recent version of the Declaration of Helsinki, and that the Study data are credible, reliable and reproducible.

The Investigator and Trial team acknowledge and agree that prospective, planned deviations or waivers to the protocol are not permitted under applicable regulations on clinical studies. However, should there be an accidental protocol deviation, such deviation shall be adequately documented in the source documents and on the relevant forms and reported to the CI and Sponsor. Deviations should also be reported to the EC as part of the EC's continued review of the Trial (e.g. through the ASR, APR, etc.). Protocol deviations which are found to frequently recur, will require (immediate) action. The Investigator acknowledges that such recurring protocol deviations could potentially be classified as a serious violation of ICH and/or the protocol.

It is understood that "a serious violation" is likely to affect to a significant degree:

- the safety or physical or mental integrity of the Trial participants; or
- the scientific validity of the Trial

The Investigator is expected to take any immediate action required to protect the safety of any participant included in the Trial, even if this action represents a deviation from the protocol. In such cases, the Sponsor should be notified of this action and the EC at the Trial site should be informed according to local procedures and regulations.

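### Section 4.5 swaps the blood tests of the routine and study-specific visits relative to the flowchart, and so schedules no HbA1c, kidney, liver, thyroid or uric acid test at intake

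*Protocol*

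**What the plan says.** Section 4.5 names five in-clinic visits with a blood draw. Intake, week 16 (W16) and week 52 (W52) are routine; week 10 (W10) and week 26 (W26) are study-specific. For the first group it says: "During the routine visits, only fasting glucose and lipid levels (LDL-cholesterol, HDL-cholesterol, triglycerides) will be assessed in the blood". It then adds HbA1c, liver, kidney and thyroid tests and uric acid at the second group. It closes with: "For a detailed overview of the visit schedule, please refer to the Study Flowchart".

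The flowchart has a row for each of these tests, for example "Kidney function: creatinine, eGFR". The five extended rows are marked at V2 (start), V12 (W16, routine) and V16 (W52, routine). Fasting glucose and lipids are marked at all five visits.

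Three other places bear on which text is right:

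- The budget has one laboratory line per site, beginning "Study specific lab tests (fasting glucose, lipids", with 62 samples each.
- Inclusion criterion 5 requires: "No history, no drugs, HbA1c < 6,5% and FPG <126 mg/dl". Exclusion criterion 8 reads: "Contraindication for VLCKD, including CKD stage 4-5, liver cirrhosis, type 1 diabetes mellitus, active gout".
- Section 2.4 sets the order: "The inclusion and exclusion criteria will be checked and afterwards patients will be randomized".

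**The concern.** Section 4.5 tells site staff which tubes to draw at which visit, and it contradicts the flowchart that it refers to. A site working from section 4.5 would have no scheduled baseline for kidney, liver, thyroid, uric acid or HbA1c values in patients about to start naltrexone/bupropion, half of them also an 800 kcal diet. An abnormal creatinine or liver value at W10 would then have no scheduled in-study value to compare with.

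The secondary objective is to describe changes in metabolic health parameters. A change in HbA1c or uric acid cannot be described without a baseline, although neither is a listed endpoint.

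Section 8.4 adds: "The Study must be performed in accordance with the protocol". With two schedules in one protocol, following either one departs from the other. If the two sites followed different texts, their extended-panel data would have no time point in common.

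**Working it through.** No sample size or power figure is involved. The check sets the texts side by side and counts.

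**Step 1: the extended panel.** HbA1c (1), liver (6), kidney (2), thyroid (2), uric acid (1): 1 + 6 + 2 + 2 + 1 = 12 analytes in 5 flowchart rows.

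**Step 2: where each text puts it.**

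| Visit | Section 4.5 | Flowchart |
|---|---|---|
| Intake / V2 | no | yes |
| W10 | yes | no |
| W16 | no | yes |
| W26 | yes | no |
| W52 | no | yes |

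The texts disagree at 5 of 5 visits, which is 5 rows × 5 visits = 25 of 25 cells. All 25 come from one exchange of two lists. For glucose and lipids, 2 rows × 5 visits = 10 of 10 cells agree.

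In the available copy of the flowchart, the last marks of the laboratory rows sit one column too far right: the final HbA1c mark falls in column 17 of a 16-visit table. Assigning these marks to W26 and W52 is therefore an inference. The marks at V2, W10 and W16 read directly, and V2 alone contradicts section 4.5.

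**Step 3: panels scheduled for 62 patients.**

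- Flowchart: 62 × 3 = 186, of which 62 at baseline.
- Section 4.5: 62 × 2 = 124, of which 0 at baseline.

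**Step 4: which text is right.**

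- Budget: (62 + 62) samples / 62 patients = 2 per patient, which matches two study-specific visits. The tests named are glucose and lipids only. The amounts reproduce: 62 × 10.86 = EUR 673.32 and 62 × 21.54 = EUR 1,335.48, together EUR 2,008.80. Section 4.5 would put the extended panel at exactly these two visits, and no budget line names it there.
- Eligibility: inclusion criterion 5 needs an HbA1c value at entry, and exclusion criterion 8 needs kidney and liver status. The flowchart marks no laboratory test at V1, so V2 is the only scheduled draw that could inform either. Section 4.5 takes HbA1c and creatinine out of it.

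Both point to the flowchart as the intended schedule.

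**Step 5: timing under section 4.5.** The first extended panel falls at W10, day 10 × 7 = 70. The ±30-day window gives days 40 to 100. The strict phase in Appendix 2 lasts 4 weeks and ends on day 28. Even the earliest permitted draw comes 40 − 28 = 12 days after it.

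**The case against.** The strongest reply is that eligibility does not depend on this error. Even under the flowchart, the first blood is drawn at V2, and section 4.3 randomizes at the initial study visit. Unless results return the same day, HbA1c and creatinine from V2 come too late for allocation under either text. Fasting glucose, also required by inclusion criterion 5, has the same timing in both. The criteria bind the site whatever section 4.5 says, and exclusion criterion 8 lists diagnoses and not laboratory thresholds. This stands in part: correcting section 4.5 does not by itself guarantee results before randomization, and a site may rely on earlier routine results, although the protocol does not say so. The loss of the baseline panel remains.

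It can also be said that section 4.5 is a summary that defers to the flowchart. It does refer to it for the detailed schedule, but it gives no order of precedence and states its own content with the word only. Section 2.4 also points to an Appendix 4 for the parameters collected. The contents list ends at Appendix 3, so that source cannot be checked.

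Divergence between the sites is hypothetical: one PhD student is accountable for both, and the sponsor provides a common eCRF. Against that, section 7.3 does without independent monitoring, so that safeguard would not catch it.

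Finally, no analyte of the extended panel is a listed endpoint. That is correct and limits the weight of the point.

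**Conclusion.** The concern holds. Section 4.5 is wrong as written: it inverts the flowchart for the extended panel at all five blood draws and removes all 62 baseline panels. The V2 and W16 marks and the budget establish this without the shifted columns.

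The consequences are confined to the baseline and safety follow-up of the extended panel and to the laboratory support for eligibility, and they arise only where a site follows section 4.5. Weight at 26 weeks, the sample size, and the glucose, lipid and blood pressure endpoint are not affected. The panel counts assume that all 62 patients attend every visit.

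**What to change.** Exchange the two test lists in section 4.5, for example:

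> At the routine visits (intake, W16, W52), blood is tested for fasting glucose, lipids, HbA1c, liver, kidney and thyroid function, and uric acid. At the study-specific visits (W10, W26), it is tested for fasting glucose and lipids only. Where this section and the Study Flowchart differ, the flowchart applies.

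Leave the flowchart and the budget as they are.

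The cost is a change of wording. Compared with the flowchart, it adds no visit, blood draw or assay, and the study-specific laboratory budget stays at EUR 2,008.80. The 124 extended panels that section 4.5 now places at W10 and W26 are no longer called for. Patients already tested only at those visits would still lack a baseline, and this should be recorded.
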